All NSCLC patients attending the responsible department of treating this type of patients (e.g. Oncology Department, Pulmonology Department) for the first time (regardless of whether the patient is diagnosed with locally, advanced or metastatic disease) at the participating sites

Version No: 4.0 Date: 8 December 2009

from the first of January 2010 to the end of July 2010. Patients diagnosed, or even treated, in other departments within the same hospital or in another hospital are susceptible to be included in the study if full access to the patient's medical record is made available.

Methods

The inclusion period will last 6 months, from the 1st of February 2010 to the 1st of August 2010. All patients attending the responsible department of treating this type of patients for the first time during this period should be included in the study. Patients could be retrospectively included in case of not receiving the Ethics Committee approval by the first of January 2010, but only those patients attending for the first time during the enrolment period.

The follow-up period will last for at least one year (the follow-up period will be conducted until the end of July 2011, so the maximum follow-up period will comprise 18 months) or until the patient is deceased, lost to follow-up or changed to another hospital.

Information regarding patients and disease characteristics as well as clinical management approach (diagnostic methods, treatments and follow-up patterns) and final outcomes will be taken from the medical record at each evaluation visit. These visits will be performed according to normal clinical practice.

Functional status and Quality of Life (QoL) questionnaires will be collected directly from the patients immediately after obtaining informed consent.

All patients regardless of whether they are participating in clinical trials or not are eligible to be included in the study. This is a purely observational study, therefore participation in this study will not interfere with participation in a clinical trial.

Statistical Analysis

A descriptive analysis approach will be used to analyse NSCLC population, clinical management, clinical outcomes and use of health care resources.

Version No: 4.0 Date: 8 December 2009

TABLE OF CONTENTS

PAGE

SUMMA	RY OF THE NON-INTERVENTIONAL STUDY PROTOCOL	2
TABLE (OF CONTENTS	8
LIST OF	ABBREVIATIONS AND DEFINITION OF TERMS	11
1.	INTRODUCTION	13
1.1	Background and rationale	13

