3. STUDY PLAN AND PROCEDURES

3.1 Overall study design and flow chart

This is a multinational, multicentre, non-interventional, prospective cohort study to be carried out in a representative selection of hospitals in order to assess lung cancer management in countries throughout Central Eastern Europe and Russia. Within the scope of this study, no diagnostic or monitoring procedures in addition to the routine procedure will be applied to the patients.

To ensure a valid picture of real life management, sites will be selected focusing on representative hospitals where lung cancer patients are being managed, in all participating countries.

All NSCLC patients attending the responsible department of treating this type of patients (e.g. Oncology Department, Pulmonology Department) for the first time (regardless of whether the patient is diagnosed with locally, advanced or metastatic disease) at the participating sites from the first of January 2010 to the end of July 2010. Patients diagnosed, or even treated, in other departments within the same hospital or in another hospital are susceptible to be included in the study if full access to the patient's medical record is made available.

Patients could be retrospectively included in case of not receiving the Ethics Committee approval by the first of January 2010, but only those patients attending for the first time during the enrolment period.

Information regarding patient and disease characteristics will be taken from the medical record, as well as management approaches regarding the visit plan, diagnostic tests performed and therapies received by the patient.

A sample of patients will be invited to complete Quality of Life questionnaires when coming to the responsible department of treating this type of patients for assessment. PROs will be collected at each evaluation visit from the first visit (diagnosis) to last visit (after 12 months). PROs will not be completed at treatment administration visits and/or disease- or treatment-related event visits.

The data source for this study will be the medical record at the responsible department of treating this type of patients for each patient. Neither visits nor interventions will be carried out for the study purposes.

Protocol of Non-Interventional Study Drug Substance: N/A

NIS Code: NIS-ORU-IRE-2009/1

Version No: 4.0 Date: 8 December 2009

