The eCRF will be completed at each evaluation visit, entering information on this visit and any other relevant data related to any intermediate visits between the last evaluation visit and the current visit. The study termination module of the eCRF must be completed at the time the investigator is aware of patient's death or withdrawal.

Figure 1 Study flow chart

[figure not shown]

Table 1 Study plan

Time	Inclusion assessment	Each evaluation visit
Informed Consent (when necessary)	X	
Patient Demographics	X	
Site information*	X	
Smoking habits	X	
Disease Information	X	X
Diagnosis information	X	
Therapy information	X	X
Clinical outcomes		X
Events due to therapy and/or disease		X
Adverse events due to therapy		X
Use of resources	X	X
Patient Reported Outcomes (a sample of patients)	X	X

Version No: 4.0 Date: 8 December 2009

Time	Inclusion assessment	Each evaluation visit
Study termination (when investigator is aware)		X

^{*}At the time of registering a participating site

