3.3.3 Discontinuation of patients from assessment

3.3.3.1 Criteria for Discontinuation

The following criteria for withdrawal only apply to patients who, according to local regulations, need to sign the ICF in order to participate in this study. Thus these criteria apply to all patients included in the PRO sample, and to all patients when the ICF is required for all participating subjects:

- 1. Voluntary withdrawal by the patient who is free to withdraw from this NIS at any time, without prejudice to further treatment.
- 2. Severe non-compliance with questionnaire instructions as judged by the investigator and/or AstraZeneca's local coordinator.
- 3. required Inadequate enrolment e.g., the patient does not meet the inclusion/exclusion criteria for the study.

3.3.3.2 **Procedures for discontinuation**

Patients who wish to withdraw from the PRO sub-study will be immediately withdrawn but the information from the medical record will continue to be collected $^{\bar{I}}$.

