4.1.2 Information regarding clinical management

Site description and characteristics: In order to describe the main characteristics of the sites providing health care for NSCLC patients. This variable will be not collected for each patient, but for each site involved in the study. This information will therefore be collected at the time of registering a participating site.

Type of hospital: Teaching hospital, research centre.

Protocol of Non-Interventional Study Drug Substance: N/A

NIS Code: NIS-ORU-IRE-2009/1

Version No: 4.0 Date: 8 December 2009

Diagnosis Procedures: This is one of the key factors in NSCLC patient management. These variables will allow us to determine how patients arrive at the department responsible of treating this type of patients, and how they have been managed during the period of time from the occurrence of the first symptom to the first therapy prescribed. Information will therefore be recorded regarding:

- Date of diagnosis.
- Disease-related triggering symptoms at diagnosis (Dyspnoea, Asthenia, Chest Pain, Cough, Dysphagia, Haemoptysis).
- Diagnostic technique(s).
- Date of first consultation about symptoms.
- Biomolecular determinations performed or not.
- Any other test performed for diagnostic purposes.

Therapy information: As with diagnosis, therapy is a key factor in terms of lung cancer patient management. The following variables will be collected to this end:

- Surgery: Performed or not and for explorative and/or resection purposes.
- Chemotherapy: onset date, end date, cycles, drug, best response and related adverse events when applicable. Any drugs involved in clinical research will be recorded as "clinical research drug" and onset date, end date and best response will be also collected.
- Radiotherapy. Onset date, end date, type, best response, and related adverse events.
- Other therapy received. Onset date, end date, type, best response and related adverse events. Also supportive care for anaemia should be included in this group: transfusions, erythropoetin, etc.

Use of health resources: This variable is closely related with the previous two, since diagnosis and therapy cover most of the time the patient is in contact with the professional responsible of treating this patients. All variables described above will be used to describe the use of health resources, and the following will also be collected:

- Date of each visit.

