6.2 Analysis of outcome variables in relation to objectives and hypotheses

Three groups will be created from baseline evaluation for the purpose of data analysis. The patients will be divided according to the baseline stage of their disease (non-advanced NSCLC patients, locally advanced NSCLC patients and metastatic NSCLC patients). For each of them the following variables will be considered:

- Clinical evolution from baseline to each visit:
 - o Changes in number of disease-related symptoms.
 - o Changes in the extent of the disease.
- Treatment response from baseline to each visit:
 - o Number of patients with complete response to treatment.
 - Number of patients with partial response to treatment.
 - Number of patients with stable disease under treatment.
 - o Number of patients with progression of disease after treatment.
 - O Progression-free time from the last progression or diagnosis to new progression of disease during the study period. The main analysis of the time to disease progression will be a Cox proportional hazards model to estimate the hazard ratio of progression among the analysis groups, with 95% confidence intervals. This will be a 2-sided test of the hypothesis, with a statistical significance level of 0.05. The assigned treatment will be included as a covariate.
- Treatment-related events.

Protocol of Non-Interventional Study

Drug Substance: N/A

NIS Code: NIS-ORU-IRE-2009/1

Version No: 4.0 Date: 8 December 2009

> o Mean number of patients with any treatment related event during the study period.

> o Mean number of patients with any serious treatment related event during the study period.

Mortality.

- o Number of patients with documented death during the study period.
- o Number of patients with a documented death due to NSCLC during the study period.

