6.3 Method of statistical analysis

Considering the study objectives, the analysis strategy will be as follows:

A descriptive analysis approach will be used to analyse NSCLC population, clinical management, clinical outcomes and health care resources.

Descriptive statistics will include frequency tables (n, mean, median, standard deviation, minimum and maximum for continuous variables and n, frequency and percentage for categorical values).

The assessment of different associations will be as follows:

Logistic and general linear models (GLM) will be used to assess the association of patient characteristics (including stage of disease, histology, PS, etc) and clinical management (independent variable) with clinical outcome variables (clinical evolution, treatment related events, mortality). The interest will separately focus on the treatment differences between each of them or a group of them used. Model-based point estimates of odds ratios and corresponding 95% confidence intervals will be reported (when applicable). P-values will be reported for comparisons between different treatments.

A descriptive analysis approach will be used to assess factors related with the use of health care resources, and a comparison of the level of use of health care resources will also be made.

The assessment of quality of life will be as follows:

Changes in FACT-L total score from first visit to the visit prior to a specific treatment response with focus on treatment differences. This is a variable of particular interest and will be analysed using an ANCOVA model.

Changes in FACT-L total score from first visit to each assessment will be analysed using an ANCOVA model.

Version No: 4.0 Date: 8 December 2009

Changes in EQ-5D total score from first visit to the visit prior to a specific treatment response with focus on the differences between treatments. This is a variable of particular interest and will be analysed using an ANCOVA model.

Changes in EQ-5D total score from first visit to each assessment will be analysed using an ANCOVA model.

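### Loss to follow-up and change of hospital end follow-up but do not trigger the eCRF termination module, so these patients cannot be identified and the mortality analyses in effect count them as alive.

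*Protocol*

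**What the plan says.** The Methods part of the protocol summary runs follow-up for at least a year, to the end of July 2011, "or until the patient is deceased, lost to follow-up or changed to another hospital". That makes three early stops.

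Section 3.1 ties the eCRF termination module to a different pair of events. It "must be completed at the time the investigator is aware of patient's death or withdrawal". Table 1 has a termination row, marked in the evaluation-visit column and conditional on the investigator's awareness, but it names no reasons.

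Section 3.3.3.1 gives the only list of withdrawal reasons: the patient's own decision, severe non-compliance with the questionnaires, and inadequate enrolment. It limits its own scope: "The following criteria for withdrawal only apply to patients who, according to local regulations, need to sign the ICF".

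On data, section 3.1 states: "The data source for this study will be the medical record at the responsible department of treating this type of patients for each patient". Section 4.1.2 lists "Date of each visit" among the items collected.

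On analysis, the first mortality variable in section 6.2 is "Number of patients with documented death during the study period". Section 6.3 names mortality among the clinical outcomes to be related to patient and management factors by logistic and general linear models. Section 6.2 plans a Cox model for progression.

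**The concern.** Two of the three early stops leave no required trace. A patient who transfers or is lost simply stops generating evaluation visits. Visits follow routine practice rather than a fixed schedule, so a gap does not show that the patient has left. A patient alive at the cut-off does not trigger the module under section 3.1 either, so lost, transferred and still-followed patients can look the same in the database. Section 5.1 adds that source data are not verified and data are not monitored, so little would bring the gap to light.

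Mortality is at stake. A death after the patient leaves the treating department is unlikely to enter that department's record. A count of documented deaths, or a yes/no model built on it, then takes the patient as a survivor. Section 2.1.2 makes differences in clinical outcomes between countries an analytical objective, so unequal loss between groups could pass for a difference in mortality.

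**Working it through.** **The plan's own figure.** The only stated number that touches this point is the 18-month maximum follow-up. From 1 February 2010 to 31 July 2011 is 17.9 months, which reproduces it. From the 1 January 2010 start that the protocol also gives, it would be 18.9 months. Nothing below depends on which is used.

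**Exits side by side.**

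| Exit | Ends follow-up (Summary, Methods) | Triggers module (3.1) | Listed as withdrawal (3.3.3.1) |
|---|---|---|---|
| Death | yes | yes | not applicable |
| Loss to follow-up | yes | not named | no |
| Change of hospital | yes | not named | no |
| Withdrawal | not named | yes | yes, only where consent must be signed |
| Alive at end of July 2011 | yes | not named | no |

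**What the data still allow.** Every visit is dated, so each patient has a last dated contact. Progression is judged at evaluation visits, so the Cox model can be censored at the last one. What is missing is a required reason and date for leaving, and any statement of vital status at that point.

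**Illustration for mortality.** Inputs: one-year survival of 35% (section 1.1, stage IIIB/IV on first-line chemotherapy), an exponential survival curve (assumed), and a 12-month loss or transfer proportion L (assumed, since the protocol gives none). True 12-month mortality is then 65%.

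1. Hazard: h = −ln(0.35)/12 = 1.0498/12 = 0.0875 per month.
2. Suppose departure times are spread evenly over 12 months. The chance that a departing patient is alive on leaving and dead by month 12 is the mean of exp(−hu) − 0.35 over u from 0 to 12, which is 0.65/1.0498 − 0.35 = 0.619 − 0.35 = 0.269.
3. Deaths missed = 0.269 × L. For L = 5%, 10% and 20% this is 1.3, 2.7 and 5.4 percentage points.
4. For scale, the standard error of a 65% proportion in the 500 patients planned for Russia is √(0.65 × 0.35/500) = 2.1 points.

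**Check with another loss model.** Let loss be exponential with rate m = −ln(1 − L)/12. Documented mortality = h/(h + m) × [1 − 0.35 × (1 − L)]. For L = 10%, m = 0.0088, giving 0.909 × 0.685 = 0.623.

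| L | Documented mortality | Missed |
|---|---|---|
| 5% | 63.6% | 1.4 points |
| 10% | 62.3% | 2.7 points |
| 20% | 59.4% | 5.6 points |
| 30% | 56.4% | 8.6 points |

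**Effect on a comparison.** Take two groups with the same true mortality but 5% and 20% loss. The odds of documented death are 0.636/0.364 = 1.75 and 0.594/0.406 = 1.46, a spurious odds ratio of 0.84. With 10% and 30% loss the same calculation gives 0.78.

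**The case against.** The best defence is that this is loose wording. Section 3.1 says when the module must be completed; it does not forbid completing it for other exits, and Table 1 does not restrict the reasons. Section 3.3.3.1 limits itself to patients who must sign consent, so it may not define the withdrawal meant in section 3.1, which could be read as any exit. The eCRF, its instruction manual and Figure 1 are not shown. Censoring rules and denominators usually belong in the SAP, which section 6.1 promises before database lock.

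Much of this is fair. The eCRF may well offer more reasons than the protocol names, and the protocol nowhere says in words that departed patients count as alive. What remains is that the protocol lists two different sets of exits and requires a record for only one of them. A SAP can set a censoring rule, but it cannot supply a reason for leaving or a vital status that sites were never required to enter.

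The illustration is also open to attack. The 35% refers to treated stage IIIB/IV disease, while section 3.3.2.1 admits all stages, and the loss rates are invented. Section 6.4 does assume that 80–90% of NSCLC is diagnosed at stage IIIb/IV, so the figure is not remote. But in step 2 the hidden share shrinks as survival rises above 35%. The calculation shows direction and rough scale and is not an estimate.

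Finally, a form will not reveal deaths after transfer. That is true: the form allows those patients to be censored rather than counted as survivors.

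**Conclusion.** The mismatch is real and should be corrected. Followed as written, the protocol does not require loss or transfer to be recorded, and its mortality count and models have no time at risk. They therefore treat departed patients as non-events. The bias in mortality is downward whenever some of them die unseen, and comparisons are distorted if loss differs between groups. Its size is unknown. The 1.3 to 5.4 points rest on an assumed 5 to 20% loss, exponential survival and an advanced-stage survival figure.

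Three stronger readings are not supported:

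- A reader might infer that lost and transferred patients have no end date at all. Section 4.1.2 collects visit dates, so a last contact can be derived.
- A reader might infer that the Cox model for progression cannot be run properly. It can be censored at the last evaluation visit.
- A reader might expect the bias to be worst at referral hospitals that send patients back to local care. The protocol describes no such pattern.

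**What to change.** Reconcile the Methods part of the summary, section 3.1 with Table 1, and section 3.3.3.1. Require the termination module for every patient at death, withdrawal, loss to follow-up, change of hospital or the July 2011 cut-off. It should record the reason, the date last known alive and the date of the last disease assessment.

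In sections 6.2 and 6.3, analyse mortality as time to event, with patients at risk only up to the date last known alive, instead of as a simple yes/no outcome. Censoring assumes that leaving is unrelated to prognosis; the recorded reasons would let that be examined.

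The cost is one changed eCRF instruction and a few fields taken from the record, with no added visits and slightly more site work at study end. Deaths after transfer stay unseen but are no longer counted as survival.

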3.2 Rationale for Study Design

The EPICLIN study is designed to provide information on the clinical effectiveness of existing products, on health care resources that are associated with existing therapy and on patients' quality of life. This study is the first study to look at the treatment regimens of all lines of treatment across several Central Eastern European countries and Russia to identify patterns of care that may be similar or different across Central Eastern Europe and Russia, to make comparisons among treatments and countries and help to determine effective and cost-effective treatments in the real practice.

The EPICLIN study will provide accurate and reliable scientific information on NSCLC clinical management across Central Eastern Europe and Russia, in order to detect unmet medical needs connected to this disease.

A representative sample of the whole NSCLC population will be involved in order to achieve this objective, therefore sample selection is critical. Avoiding selection bias is essential in this study. Appropriate site selection and the inclusion of all patients attending a specific department responsible of treating this type of patients are also essential requirements.

Moreover, it is very important that the disease management pattern is not modified with respect to that of normal clinical practice. Therefore, no extra visits or extra procedures will be performed for study purposes.

Conducting this study with this design will provide high external validity, not only from a scientific point of view, but also regarding healthcare administration and healthcare providers.

This study will thus help to address a number of issues regarding the burden of NSCLC and the variability of treatment and outcomes throughout Central Eastern Europe and Russia in real practice.

3.3 Selection of patient population

3.3.1 Investigators

Patients will be recruited by clinicians working at the responsible department of treating this type of patients where he/she is being treated for his/her lung cancer. All or some of the investigators of each site could be included.

The number of participating investigators will be that needed to ensure the inclusion of the number of subjects calculated for the sample size.

Version No: 4.0 Date: 8 December 2009

The selected investigators must be representative of the whole responsible clinicians of treating this type of patients in each country and should not be selected based on any other criteria, in order to avoid any selection bias.

There is no minimum or maximum number of patients per investigator. Each investigator should invite all patients coming to his/her clinic for the first time, to participate in the study, if inclusion/exclusion criteria are met.

